4.5 Patient Withdrawal and Discontinuation

Patients may be discontinued from study treatment and assessments at any time in the following situations.

- Patient decision. The patient is free at any time to discontinue treatment, without prejudice to further treatment.
- Severe non-compliance to protocol, as judged by the Investigator and/or AstraZeneca.
- Safety reasons, eg, AE that warrants discontinuation, as judged by the Investigator and/or AstraZeneca.
- Incorrect enrolment (ie, the patient does not meet the required inclusion/exclusion criteria) for the study.
- Patient lost to follow-up.
- Pregnancy.
- Major hypoglycaemic events.

Subjects should not be discontinued from any treatment phase based on single episodes of hypoglycaemia or symptoms of hypoglycaemia unless clinically indicated (see the criteria below). The assessment of a single fingerstick or local laboratory glucose value should not be the sole assessment used to determine patient discontinuation due to hypoglycemia.

Subjects should be discontinued from study drug if they experience severe hypoglycaemia as defined by the American Diabetes Association:

- Requires assistance of another person to actively administer carbohydrates, glucagon, or take other corrective actions.
- Plasma glucose concentrations may not be available during an event, but neurological recovery following the return of plasma glucose to normal is considered sufficient evidence that the event was induced by a low plasma glucose concentration.
- Suspected/potential diabetic ketoacidosis based on Investigator's judgement.
- Patients who show a greater than 50% increase in serum creatinine on Day 4 should be discontinued from the study drug.

In all cases, the reason(s) for withdrawal and the primary reason must be recorded on electronic case report form (eCRF). If a patient is prematurely withdrawn from the study treatment for any reason, the Investigator must make every effort to perform the evaluations described for Visit 8.

Patients will also be withdrawn if the entire study is terminated prematurely as described in Section 9.10.

Refer to Section 4.3 for rescreening of patients for the study.

4.6 Planned Sample Size and Number of Study Centres

We plan to enroll a total of 51 patients at up to 5 study centres in 3 equal sized groups. Each group will enroll 17 patients. It is planned to enroll patients in Europe. Refer to Section 8.6 for sample size justification.

4.7 Patient Identification and Randomisation

4.7.1 Patient Identification

At Screening, each patient will receive a unique enrolment number. Patients who drop out of the study before dosing will retain their assigned enrolment number.

The enrolment number will be in the following format and will be recorded in the eCRF:

E code format (E Site ID Patient ID), eg, E0010001.

The enrolment number will serve as the patient identifier throughout the study and will be required in all communication between the Investigator or designee regarding a particular patient.

4.7.2 Randomisation Scheme

There is no randomisation in the study.

4.7.3 Allocation of Patients to Treatment

Start of treatment will occur at Visit 4 (Day 1) after all Screening procedures have been performed and eligibility for the study confirmed. Patients will be enrolled to specific groups based on their diagnosis. When 17 patients have been enrolled to each specific patient group enrolment into that group will stop.

5 STUDY DRUG

5.1 Identity

Dapagliflozin is a highly potent, selective and reversible inhibitor of SGLT2.

5.1.1 Investigational Products

For this study, study treatment refers to dapagliflozin 10 mg tablets.

Details of the study treatment can be found in Table 1. Dapagliflozin 10 mg tablets will be supplied by AstraZeneca in labelled bottles containing 35 tablets.

Table 1:	Identity of the Study D	rug	
Study drug		Dosage form and strength	Manufacturer
Dapagliflozin		Plain, green, diamond-shaped, film coated tablet, 10 mg	AstraZeneca

Details of the batch numbers will be included in the Trial Master File and the final clinical study report (CSR).

5.2 Administration

The study consists of a 2-week, open label, Treatment Period. Patients will be provided with one bottle of dapagliflozin tablets on Day 1 (Visit 4) to last for the 14 ± 1 days of the Treatment Period.

The tablet is taken orally once daily in the morning and at approximately the same time of the day.

There are no restrictions regarding timing in relation to food. Dapagliflozin tablets contain lactose, which may cause discomfort in lactose-intolerant individuals.

The first dose of dapagliflozin will be administered at Visit 4 (Day 1) at the study site after all baseline assessments (including laboratory tests, plasma volume assessments, and bioimpedance spectroscopy measurement) have been performed.

On days of study site visits where blood sampling is scheduled, ie, Visit 5 and Visit 8, the patients will be required to bring the bottle of dapagliflozin tablets to site. At Visit 5 (Day 4), the patient will consume the tablet together with breakfast after fasting blood sampling is completed at the site. At Visit 8 (Day 14), the patient will consume the tablet together with breakfast after pre-dose bioimpedance spectroscopy measurements, pharmacokinetics blood sampling, CC

5.3 Packaging, Labelling, and Storage

Patients will be provided with study drug according to the study plan Table 5 (Group 1) and Table 6 (Group 2 and Group 3).

The study drug will be packaged by AstraZeneca or designee according to Good Manufacturing Practice (GMP).

Labels will be prepared in accordance with GMP and local regulatory guidelines. The labels will fulfil GMP Annex 13 requirements for labelling. Label text will be translated into local language.

The study drug should be kept in a secure place under appropriate storage conditions. The study drug label on the bottle specifies the appropriate storage.

5.4 Blinding and Breaking the Blind

This is an open label study and hence blinding is not applicable.

5.5 Drug Accountability

The study drug provided for this study will be used only as directed in the study protocol. The study personnel will account for all study drugs dispensed to and returned from the patient.

The Investigator is responsible for making sure:

- That the study drug is handled and stored safely and properly (see Section 5.3).
- That the study drug is only dispensed to study patients in accordance with this protocol.

Patients should return all unused study drug and empty containers to the Investigator.

At the termination of the clinical study or at the request of AstraZeneca, remaining drug and packaging of used study drug after final drug accountability, are to be destroyed locally in line with local regulations. On destruction of the study drug at the site, the site personnel will account for all unused study drug and for appropriate destruction documentation. Certificates of delivery, destruction and return should be signed and archived.

Each dispensing and returning of study drug will be documented in the eCRF.

5.6 Compliance

Patients will be instructed on proper use of study drug.

Compliance with study treatment will be monitored via the drug accountability assessments (tablet counts at Visit 8) and patient diary entries (ie, patients will record study drug intake daily in the food questionnaires and this will be reviewed at the clinic visits during the Treatment Period).

5.7 Previous and Concomitant Medications

Any medication the patient takes other than the study treatment, including herbal and other non-traditional remedies, is considered a concomitant medication.

All concomitant medications must be recorded in the eCRF. The following information must be recorded in the eCRF for each concomitant medication: generic name, route of administration, start date, stop date, dose, regimen, and indication.

Any changes in the dosage or regimen of a concomitant medication must be recorded in the eCRF.

At Screening, patients will be asked what medications they have taken during the last 3 months. At each subsequent study visit, patients will be asked if there have been any changes to their concomitant medications or standard of care medication for T2DM or renal failure (as applicable), and whether they have taken any other medications since the previous visit.

5.7.1 Allowed Concomitant Medications

Background therapy for T2DM and renal failure:

All patients will continue to use their ARB or ACEi at the same dose that they were on prior to start of the study.

Diabetic patients will continue on metformin or sulphonylurea, or metformin+sulphonylurea therapy at the same dose that they were on prior to start of the study. For patients on insulin (Group 1), recording of total insulin doses will be done during the study.

At each visit, the Investigator will reassess whether the concomitant medication that the patient is taking is part of the original maintenance for T2DM or renal failure or whether the patient has started taking extra concomitant medication. The status of each concomitant medication (ie, pre-existing or new) will be documented on the eCRF.

Therapies for treatment of other comorbidities are allowed as long as the dose regimen is stable in the 3 months prior to first dose and is not a prohibited medication (Section 5.7.2). All efforts should be made to keep the dose of study drug stable throughout the study.

5.7.2 Prohibited Concomitant Medications

Refer to Section 4.2 for exclusion criteria relating to prohibited medications.

The following medications are prohibited during the study:

- Immunosuppressive or other immunotherapy for primary or secondary renal disease.
- Diuretic drugs including loop diuretics, thiazides, mineralocorticoid receptor antagonists.
- Use of any anti-diabetic medications with the exception of metformin, sulphonylurea and insulin (insulin only allowed in Group 1), oral glucocorticoids, NSAIDs, immune suppressants, chemotherapeutics, antipsychotics, TCAs and monoamine oxidase inhibitors.
- Use of medicinal products and substances that can reduce or increase absorption of indocyanine green: anticonvulsants, bisulphite compounds, haloperidol, heroin, meperidine, metamizol, methadone, morphium, nitrofurantoin, opium alkaloids, phenobarbital, phenylbutazone (reduced absorption), and cyclopropane, probenecid, rifamycin (increased absorption).

5.7.3 Non-investigational Product

The product used for plasma volume measurements (indocyanine green) is considered a non-investigational product (see Section 6.1.3 for details).

6 VARIABLES AND METHODS OF ASSESSMENT

6.1 Efficacy Variables

Assessments will be performed in accordance with the Study Plan (Table 5 [Group 1] and Table 6 [Group 2 and Group 3]).

6.1.1 24-hr Urine Measurement

24-hr urine collection will be performed as per schedule provided in Table 5 and Table 6. The patients will be provided with equipment for collection and storage of urine samples. Patients receive empty 24-hr urine collection containers preceding the collection days according to instructions. At the Screening Visit, patients will be instructed to start collection of urine samples starting Day -3. The morning the patient starts with the 24-hr urine collection, the bladder is emptied. The 24-hr urine collection starts after the first morning urine is voided in the toilet. The urine is collected in the container for 24 hrs. The date and time of the start and end of the urine collection should be written on the designated labels. Patients will be advised to store the urine in the refrigerator after finishing the 24-hr urine collection until he/she delivers the urine to the clinic. The carefully sealed container will be delivered to the research nurse/physician at the day of the next clinic visit. The importance of obtaining a complete urine collection will be stressed. The patients will return the equipment on the days specified in Table 5 and Table 6.

The local laboratory will receive the urine samples and will record the volume of urine collected for every 24-hr urine sample.

For premenopausal women, the Investigator will estimate the menstrual timing and aim to avoid the 2 urine collection periods (Day -3 to 4 and Day 12 to 17) during menstruation.

6.1.2 24-hr BP Monitoring

Ambulatory blood pressure monitoring will be performed to record 24-hr systolic and diastolic blood pressure at Days -1, 4, 13, and 18.

The ABPM manual will contain more detail on the specific device and method of data capture/transfer.

6.1.3 Plasma Volume Measurements

Plasma volume will be assessed using indocyanine green distribution in the circulation. Measurements will be performed prior to dosing on Day 1 (Baseline) and following dosing on Days 4 and 14. Plasma volume will also be assessed on Day 18.

6.1.3.1 Dosage, Form Strength and Storage of Indocyanine Green

Indocyanine green (tradename Verdye, manufacturer Diagnostic Green) 5mg /mL is provided as powder for solution. Single doses of 0.25 mg/kg body weight will be administered as bolus injection. For details on storage of indocyanine green see SPC [21].

6.1.3.2 Administration of Indocyanine Green

Indocyanine green is to be reconstituted with water for injection (not solutions containing salt). See SPC [21] for more information.

After the patient is weighed, a catheter will be positioned for example in an anticubital vein for the injection of indocyanine green. A second catheter will be positioned in the contralateral arm for blood sampling.

Blood collections will start exactly 2 minutes after injection of indocyanine green and will be collected for a 3-minute period at 30 sec intervals (7 blood samples). The administration of indocyanine green is of critical importance for the quality of the plasma volume measurements. It is important that the exact time of the samples is noted. Further details can be found in the manual for plasma volume measurements.

6.1.3.3 In Case of Anaphylactic Reactions due to Indocyanine Green

The risk profile of indocyanine green is considered good, but there are reports of allergic reactions including anaphylactic reactions (see Section 1.3). Since severe anaphylactic reactions might occur, indocyanine green must only be applied under supervision of a physician. If an anaphylactic reaction should occur, immediate emergency treatment should be initiated and may include below actions as judged necessary by the physician:

- Stop further administration of indocyanine green, leave injection catheter or cannula in the vein.
- Keep airways open.
- Inject 100 to 300 mg hydrocortisone or a similar preparation by rapid intravenous injection.
- Substitute volume with isotonic electrolyte solution.
- Give oxygen, monitor circulation.
- Slowly administer antihistamines intravenously.

The following additional measures may be indicated in cases of anaphylactic shock:

- Place patient in recumbent position with legs raised.
- Rapidly substitute volume with eg, isotonic electrolyte solution (pressure infusion), plasma expanders.
- Immediately administer 0.1 to 0.5 mg adrenaline (epinephrine) diluted to 10 mL with 0.9% saline intravenously (repeat after 10 min if necessary).

6.1.4 Bioimpedance Spectroscopy Measurements (Extracellular Volume, CCI

Bioimpedance spectroscopy will be performed prior to dosing on Day 1 (Baseline) and following dosing on Days 4 and 14. Bioimpedance spectroscopy will also be performed in the Follow-up Period on Day 18. CCI

Bioimpedance spectroscopy will be assessed using the SFB7 device produced by ImpediMed.

For the bioimpedance spectroscopy, patients should void their bladder and add to the ongoing 24-hr urine collection. Patients should abstain from exercising 2 hr prior to the assessment.

An alcohol swab is used to clean the skin, allowing the alcohol to dry completely before placing the electrodes on the skin. If there is excess hair on the sites where the electrodes will be attached, not allowing proper electrode adherence, these sites will be shaved.

The patient should be put in the supine position for 5 min before the measurement. The patient should not touch any metal surfaces while in the supine position. It has to be ensured that the patient's limbs are not crossed and that the legs are completely separated. For patients who cannot effectively separate their inner thighs, it may be necessary to place insulating material (eg, a towel) between them. It has to be ensured also that the patient's arms are not touching the torso. The bioimpedance spectroscopy should be set to make 3 repeat measurements (see manual instructions for SFB7 device). The patient has to remain still and relaxed during the measurement.

When several measurements are made on the same day, the patient should not remain supine between readings. The amount of time in supine position should be the same on each assessment day and at each assessment time.

The points of contact for the electrodes should be marked on the patient's skin and the same positions used at all occasions. Preferably, electrodes should be connected to the right side of the body (hand and foot according to the manual instructions for SFB7).

It has to be ensured that the bioimpedance spectroscopy machine is charged and not connected to mains power during use.

6.1.5 Efficacy Laboratory Assessments

Table 2 presents the laboratory assessments that will be performed for evaluation of theendpoints. Refer to Table 5 and Table 6 study plan for schedule of assessments.

Instructions for collection, storage, and shipment of samples will be provided in the Laboratory Manual for samples collected at central laboratories.

	Local Laboratory	Central Laboratories
Primary and Secondary Variable	C. linn	_
Secondary Variables	- Sodium	_
24-hr urinary glucose excretion	- Glucose	-
Changes in plasma volume Dapagliflozin pharmacokinetics	-	 Plasma volume Plasma concentration of dapagliflozin
Change in 24-hr UACR	- UACR	- -
	l	
		I
	- T T	ACR=urine albumin: creatinine
ratio		tert unite albumini. creatimile

Table 2:Efficacy Laboratory Variables

6.2 Safety Variables and Safety Reporting

The Investigator is responsible for ensuring that all staff involved in the study are familiar with the content of this section.

Assessments will be performed in accordance with the Study Plan (Table 5 [Group 1] and Table 6 [Group 2 and Group 3])

6.2.1 Definition of Adverse Events

An AE is the development of an undesirable medical condition or the deterioration of a pre-existing medical condition following or during exposure to a pharmaceutical product, whether or not considered causally related to the product. An undesirable medical condition can be symptoms (eg, nausea, chest pain), signs (eg, tachycardia, enlarged liver) or the abnormal results of an investigation (eg, laboratory findings, electrocardiogram). In clinical studies, an AE can include an undesirable medical condition occurring at any time, including during Run-in or Wash-out Periods, even if no study treatment has been administered.

The term AE is used to include both serious and non-serious AEs.

6.2.2 Definitions of Serious Adverse Event

An SAE is an AE occurring during any study phase (ie, Run-in, Treatment, Wash-out, Follow-up), that fulfils one or more of the following criteria:

- Results in death.
- Is immediately life-threatening.
- Requires in-patient hospitalisation or prolongation of existing hospitalisation.
- Results in persistent or significant disability/incapacity or substantial disruption of the ability to conduct normal life functions.
- Is a congenital abnormality or birth defect.
- Is an important medical event that may jeopardise the subject or may require medical intervention to prevent one of the outcomes listed above.

For further guidance on the definition of an SAE, see Section 11.1.

6.2.3 Recording of Adverse Events

6.2.3.1 Time Period for Collection of Adverse Events

All AEs will be collected from the time of first dose throughout the study, including the Follow-up Period.

All SAEs will be collected from the time of signing the informed consent throughout the study, including the Run-in and Follow-up Periods.

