There is no reason to believe that dapagliflozin poses an undue risk of hypoglycemia in non-diabetic patients. The amount of glucose excreted in the urine depends on the total filtered glucose load (blood glucose concentration x GFR). Thus, at blood glucose levels in the low normal range, the amount of glucose excreted into the urine is not sufficient to induce hypoglycaemia (Defronzo et al, 2013 [18]). In Clinical Pharmacology studies in healthy subjects single doses up to 500 mg and multiple oral doses of 2.5 to 100 mg up to 14 days have been evaluated and have shown that dapagliflozin does not induce even a single case of hypoglycemia in non-diabetic subjects.

Patients on sulphonylurea and/or insulin at the onset of the study treatment have an increased risk of experiencing hypoglycaemic events. Blood glucose is therefore monitored at Day 4. Once patients on insulin enter the study, they will be carefully followed once starting on food boxes. Additionally, insulin dosing will be adjusted, if needed, to avoid hypoglycaema/hyperglycaemia.

In this study, indocyanine green will be used to assess changes in plasma volume. Indocyanine green has been used for decades for this purpose and has a short half-life of only approximately 3 min (Jacob et al, 2007 [19]). The risk profile of indocyanine green is considered good (Jacob et al, 2007 [18]), but there are reports of allergic reactions including anaphylactic reactions (Speich et al, 1988 [20] and Garski et al, 1978 [21]). In patients with terminal renal insufficiency, the possibility that an anaphylactic reaction occurs seems to be increased (Summary of Product Characteristics [SPC] Verdye [22]).

Assessment of **CC** (including extracellular and **CC**) will be conducted with bioimpedance spectroscopy. This is an easy to use and non-invasive technique not considered to cause any risk to the patient if following the manufacturer's instructions.

No other study procedure is considered putting the patients at risk beyond those ordinarily encountered during the performance of routine medical examinations or routine tests.

Protection against risks

This study has been designed with appropriate measures in place to monitor and minimise any of the potential health risks to participating patients. In order to ensure the safety of all patients participating in this study, AstraZeneca will conduct a real-time review of all safety information from all ongoing clinical dapagliflozin studies as they become available.

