6.2.3.3 Variables

The following variables will be collected for each AE:

- AE (verbatim).
- The date and time when the AE started and stopped.
- Intensity.
- Whether the AE is serious or not.
- Investigator causality rating against the study drug (yes or no).
- Action taken with regard to study drug.
- AE caused patient's withdrawal from study (yes or no).
- Outcome.

In addition, the following variables will be collected for SAEs:

- Date AE met criteria for a serious AE.
- Date Investigator became aware of the SAE.
- AE is serious due to.
- Date of hospitalisation (if applicable).
- Date of discharge (if applicable).
- Probable cause of death (if applicable).
- Date of death (if applicable).
- Autopsy performed (if applicable).
- Causality assessment in relation to Study procedure(s).
- Causality assessment in relation to other medication (eg, concomitant medication, background therapy).
- Description of SAE.

The intensity of the reported AEs will be assessed according to the following scale:

- Mild (awareness of sign or symptom, but easily tolerated).
- Moderate (discomfort sufficient to cause interference with normal activities).
- Severe (incapacitating, with inability to perform normal activities).

It is important to distinguish between serious and severe AEs. Severity is a measure of intensity whereas seriousness is defined by the criteria in Section 6.2.2. An AE of severe intensity need not necessarily be considered serious. For example, nausea that persists for several hours may be considered severe nausea, but not a SAE unless it meets the criteria shown in Section 6.2.2. On the other hand, a stroke that results in only a limited degree of disability may be considered a mild stroke but would be a SAE when it satisfies the criteria shown in Section 6.2.2.

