- p. Patients will receive empty 24-hr urine collection containers preceding the collection days according to instructions. Dispensing of 24-hr urine containers may occur at several occasions during the study period.
- q. ABPM will be used to record 24-hr SBP and DBP. Specific instructions will be provided to the patients as per the ABPM manual.
- r. Assessments of plasma volume and bioimpedance spectroscopy should be done in the following order: 1) CC
 Day 1, plasma volume assessment and bioimpedance spectroscopy will be performed pre-dose, while on Days 4 and 14, it will be assessed post dose.
 2) Intake of study drug and other medications and breakfast (The time when dapagliflozin is taken should be noted as t=0). 3) One hr after dapagliflozin intake, bioimpedance spectroscopy is performed (Days 4 and 14). The timing of the assessment relative to the dapagliflozin dose should be consistent across visits for each patient. 4) Approximately 1.5 hr after dapagliflozin intake, the plasma volume assessment will be done. The timing of the assessment relative to the dapagliflozin dose should be consistent across visits for each patient. 5) On Day 14, the bioimpedance spectroscopy measurement will be conducted also at pre-dose, as well as 2 and 4 hr after dapagliflozin dose (in addition to 1 hr post-dose noted above), that is, the bioimpedance spectroscopy measurement is always to be done

Study code: D1690C00049
Investigational product: Dapagliflozin
before pharmacokinetics sampling.

AstraZeneca AB

Clinical Study Protocol CONFIDENTIAL

before pharmacokinetics sampling. On Days 1 and 18, bioimpedance spectroscopy is conducted 1 hr after intake of breakfast and non-study drugs (but not dapagliflozin) and plasma volume is assessed 1.5 hr after breakfast and non-study drug intake.

- s. Bioimpedance spectroscopy measurements include assessment of extracellular volume, CCI
- t. Study drug administration should start in the morning at Day 1 (Visit 4) and last dose should be taken by the patient on Visit 8.
- u. Intake of study treatment will be confirmed based on the completion of record of drug intake by the patient in the food questionnaire on Days 4, 5, 13, and 14. Drug accountability (tablet count) will be performed on Visit 8.
- v. AEs are collected from time of first dose and SAEs are collected from provision of informed consent throughout the study.

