7.2.3 Treatment Period (Day 1 to Day 14)

7.2.3.1 Visit 4: Day 1 (Dosing Initiation Visit)

Treatment with dapagliflozin 10 mg/day will be initiated on Day 1 for eligible patients after blood sampling.

- Obtain 24-hr urine sample from previous day (ie, Day -1)
- Patient to start collection of 24-hr urine sample
- Discontinue 24-hr ABPM
- Vital signs (blood pressure and pulse)
- Body weight
- Pre-dose blood and urine samples
- Safety laboratory assessments (haemoglobin, creatinine, haematocrit, and glucose all of which [except haemoglobin] are also **CC**

CCI

-

- CCI
- Patient will have breakfast at the study site along with non-study drugs
- Bioimpedance spectroscopy measurement (pre-dose; 1 hr after food intake)
- Measurements for plasma volume (pre-dose; approximately 1.5 hr after food intake)
- Administration of first dose of study drug at the study site
- Dietary advice
- Concomitant medication
- AEs/SAEs
- Review of food questionnaires completed by the patient
- Dispensation of study drug sufficient for up to 15 days of treatment duration

Patients will be asked to follow the procedures below until the next clinic visit:

- collect 24-hr urine samples on Day 2 and Day 3
- follow dietary advice daily
- complete food questionnaires daily
- **CC** for the next clinic visit on Day 4 and to bring the study drug to the clinic for consumption after the blood sampling

7.2.3.2 Visit 5: Day 4

Following procedure will be performed at this visit:

- Obtain 24-hr urine sample from previous days (ie, Days, 1, 2 and 3)
- Patient to start collection of 24-hr urine sample
- Vital signs (blood pressure and pulse)
- Body weight
- Pre-dose blood and urine samples
- Safety laboratory assessments (creatinine, haematocrit, and glucose all of which are **CC**)
- Pre-dose blood sample for dapagliflozin pharmacokinetics
- CCI
- Patient will have breakfast at the study site along with study drug (t=0) and non-study drugs
- Bioimpedance spectroscopy measurement (1 hr after study drug intake)
- Measurements for plasma volume (approximately 1.5 hr after study drug intake)
- Start 24-hr ABPM

- Verify study treatment intake from diaries
- Dietary advice
- Concomitant medication
- AEs/SAEs
- Review of food questionnaires completed by the patient

7.2.3.3 Visit 6: Day 5

Following procedure will be performed at this visit

- Obtain 24-hr urine sample from previous day (ie, Day 4)
- Discontinue 24-hr ABPM
- Verify study treatment intake from diaries
- Dietary advice

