5.1.3 Safety variables

5.1.3.1 Adverse events

AEs and Serious AEs (SAEs), are defined in Section 6.2.1 of the CSP. SAEs will be collected from the time of informed consent until the end of the Follow-up period. All other AEs will be recorded from first dose until the end of the Follow-up period.

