5.2.6 Safety Set

All patients who took at least one dose of study drug and who have data from at least one post-dose safety assessment available will be included in the Safety Set.

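### Non-serious adverse events are recorded only from the first dapagliflozin dose, although the first of four indocyanine green injections is given before it

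*Protocol*

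**What the plan says.** **Collection window.** Protocol 6.2.3.1 states: "All AEs will be collected from the time of first dose throughout the study, including the Follow-up Period". For serious events it states: "All SAEs will be collected from the time of signing the informed consent throughout the study, including the Run-in and Follow-up Periods". The study plan footnotes (Table 5 footnote v, Table 6 footnote t) repeat this: "AEs are collected from time of first dose and SAEs are collected from provision of informed consent throughout the study". SAP 5.1.3.1 agrees on non-serious events: "All other AEs will be recorded from first dose until the end of the Follow-up period".

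**Order on Day 1.** Protocol 7.2.3.1 puts this step just before administration of the first study drug dose: "Measurements for plasma volume (pre-dose; approximately 1.5 hr after food intake". Protocol 6.1.3 also places the Day 1 measurement before dosing, and 5.2 has the first tablet follow all baseline assessments, plasma volume among them.

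**The agent.** Plasma volume is measured with an intravenous bolus of indocyanine green (6.1.3). Protocol 1.3 says of it that "there are reports of allergic reactions including anaphylactic reactions", and lists symptoms that range from itching and flushing to cardiac arrest.

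**Causality.** For every adverse event the form asks for: "Investigator causality rating against the study drug (yes or no". Under 6.2.3.3 and 6.2.3.4, causality against study procedures and other medication is added for serious events only.

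**Analysis set.** SAP 5.2.6 admits to the Safety Set: "All patients who took at least one dose of study drug and who have data from at least one post-dose safety assessment available". SAP 5.3.18 bases all safety tables, listings and figures on that set unless another is specified.

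**The concern.** Protocol 1.3 singles out indocyanine green among the study procedures: apart from it, no procedure is thought to add risk beyond routine examinations and tests. Yet the first injection falls before non-serious event collection opens, so the record of how patients tolerated the agent starts at the second of four injections.

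The missing piece is also the easiest to interpret. On Days 4 and 14 the injection is given about 1.5 hours after dapagliflozin, so a rash or flush could belong to either product, and the form asks only about dapagliflozin. Day 1 is the one injection given before any dapagliflozin.

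There is a reporting gap as well. A patient who reacts on Day 1 and is then not dosed cannot be in the Safety Set. Even a serious event in that patient would be in the database but in none of the planned safety outputs.

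**Working it through.** The plan states no figure on this point, so there is none to reproduce. The check is one of order and definitions, followed by a count.

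**1. Does first dose mean dapagliflozin?** Protocol 6.2.3.1 does not name the product, and 6.1.3.1 uses the word dose for indocyanine green too. Four places settle it:
- Protocol 5.1.1 defines study treatment as dapagliflozin tablets.
- Protocol 5.7.3 classes indocyanine green as a non-investigational product.
- SAP Section 2 starts adverse event collection at dosing.
- Protocol 7.2 lists only serious events at Visits 1 to 3; the combined adverse event entry first appears at Visit 4, after the first tablet.

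**2. Is the injection before that dose?** Yes. Protocol 5.2, 6.1.3, 7.2.3.1 and the Table 5 and 6 footnotes on plasma volume all agree. No interval between injection and tablet is stated.

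**3. Does the event definition close the gap?** No. Protocol 6.2.1 defines adverse events to include those arising when no study treatment has yet been given. The definition is wider than the collection window, and it is the window that says what is recorded.

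**4. Does any safety output reach an undosed patient?** No output under SAP 5.3.18 names a set other than the Safety Set. Such a patient would appear in disposition, which uses the Enrolled Set (SAP 5.3.9.1).

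**5. Count of injections.** Plasma volume is measured on Days 1, 4, 14 and 18, so 4 per patient. Protocol Table 4 agrees: 4 samples × 14 mL = 56 mL.
- Before the window opens: 1 of 4 = 25%.
- Groups 2 and 3 only (SAP introduction: no Group 1 enrolment): 2 × 17 = 34 patients, 34 × 4 = 136 injections, 34 outside the window.
- All three groups: 3 × 17 = 51 patients, 51 × 4 = 204 injections, 51 outside the window.

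**6. Chance that it matters.** The documents give no reaction rate. Let p be an assumed chance, per patient, of a reaction to the Day 1 injection that starts before the tablet. The chance of at least one among n patients is 1 − (1 − p)^n.

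| Assumed p | n = 34 | n = 51 |
|---|---|---|
| 0.1% | 3% | 5% |
| 1% | 29% | 40% |
| 2% | 50% | 64% |
| 5% | 83% | 93% |

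For example, with p = 1% and n = 34: 1 − 0.99^34 = 0.289. The width of the range comes entirely from the assumed rates.

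**The case against.** **Serious reactions are covered.** They are collected from consent. The definition includes important medical events, and the Appendix 11.1 examples include angioedema needing intravenous hydrocortisone and intensively treated bronchospasm. They also get a procedure causality rating and 24-hour reporting (6.2.3.4, 6.2.4). This stands. A reader might infer that the plan misses dangerous reactions; it does not. What is lost from required collection is non-serious reactions in the interval before the tablet.

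**Patients are protected at the bedside.** A physician supervises each injection with emergency equipment at hand (1.3, 6.1.3.3), and sees a reaction whether or not it is entered as an adverse event. This stands too. It would be wrong to say that staff lack warning before the later injections.

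**Renal risk.** One might argue that Group 3 (eGFR 25 to 50) is at raised risk. Protocol 1.3 ties the possible increase in anaphylactic reactions to terminal renal insufficiency, and the documents do not describe Group 3 in that way. It also calls the agent's risk profile good. The point does not rest on renal function.

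**The wording may be loose enough.** Visit 4 has an adverse event entry, and the open question in 6.2.3.5 covers health problems since the patient was last asked. A site might well record a pre-dose reaction. But neither place overrides 6.2.3.1, so recording would vary by site.

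**The Safety Set fits its purpose.** The safety objective concerns dapagliflozin, and undosed patients do not belong in its denominator. Agreed. That is a reason for a separate listing, not for redefining the set.

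**Conclusion.** The point holds as a gap in the completeness of safety data. Followed exactly, the plan does not require recording of non-serious reactions that start between the first indocyanine green injection and the first dapagliflozin dose. It does not ask whether any non-serious event was due to a study procedure. It would show a serious reaction in a never-dosed patient in no safety table or listing.

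The size is one injection in four per patient, and every patient's first exposure in the study. That is a share of injections, not of reactions lost: reactions that start after the tablet, or after the Day 4, 14 and 18 injections, are inside the window. The number of events lost cannot be estimated without a reaction rate.

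The conclusion assumes that first dose means the first dapagliflozin dose, which the documents support. The primary endpoint, its analysis and the sample size are unaffected.

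**What to change.** 1. **Window.** In protocol 6.2.3.1 and 3.2.4, the Table 5 and 6 footnotes and SAP 5.1.3.1, start collection of all adverse events at the beginning of Visit 4, before the indocyanine green injection. Bring the same statement in the protocol synopsis, 1.2.3, 7.2.1.1 and SAP Section 2 into line. This also narrows the mismatch with the definition in 6.2.1.
2. **Causality.** Extend the study-procedure causality question from serious events to all adverse events.
3. **Listing.** Add one listing of adverse and serious adverse events for all patients given indocyanine green, dosed or not. Leave the Safety Set unchanged as the dapagliflozin denominator.

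Cost: protocol and SAP wording, one extra eCRF question, one listing and a few more mild events to record. No new analysis structure is needed. Event start times are already collected (6.2.3.3), and SAP 5.3.18.1 already assigns events to screening, treatment or follow-up by start date and time, so pre-dose events can be kept apart from those on dapagliflozin.
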